3.1 Primary Outcome (Feasibility) Measures

3.1.1. Enrollment rate: The enrollment rate is the number of patients/caregivers enrolled per month. We will further determine the number of patients/caregivers screened and approached for enrollment. Based on these numbers, we will calculate the proportion of screened patients/caregivers eligible for enrollment, the proportion of eligible patients/caregivers approached, and the proportion of approached patients/caregivers enrolled. Of those not eligible, we will record reasons for ineligibility. Of those eligible, but not approached, we will record reasons. For those approached, but not enrolled, we will record reasons.

3.1.2 Drop-out rate: The drop-out rate is the proportion of enrolled participants (patients and caregivers) who drop out of the study before completion.

3.1.3 Data completion: We will record the completeness of the data collection for enrolled subjects. For those with incomplete data, we will record reasons that data could not be collected.

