3.2.5 Caregiver Burden: Caregiver burden will be obtained from the caregiver only. The Zarit Burden Interview-12 (ZBI-12) is a validated instrument that has been utilized in various populations.⁶¹ It has excellent test characteristics when compared with the long form of the ZBI, and it has been used in other studies of cirrhosis.^{4, 62}

3.2.6 Acute Health Care Utilization: Health care utilization will be obtained from the patient only. In addition to patient-reported emergency room and admission data, we will use the Indiana University Health local data warehouse and the larger Indiana Network for Patient Care (INPC) to complement the utilization assessment. INPC is a large health information exchange in Indiana and provides data from all health care systems within the state.⁶³ We will determine the number of emergency room visits and the number of hospitalizations within 6 months of discharge as well as associated diagnoses. As part of this, we will also be tracking admissions specific to COVID-19, due to the large impact the pandemic has had on our healthcare system. We will do that by tracking whether patients are admitted with a COVID-19 diagnosis or die of COVID-19 while enrolled in the study.

3.2.7 CMH Interactions: In patients/caregivers randomized to the Cirrhosis Medical Home, we will record the numbers, timing, and types of interactions with the care coordinator (in-person, phone, video, other forms of communication). We will also record the use of interventions (e.g. care protocols, pharmacologic treatments).

3.2.8 Palliative Care outcomes: Palliative care referrals will be recorded, including presence of a referral order, successful attendance at a palliative care visit, completion of advanced directives, and place of death.

3.3 Other Patient Measures: At baseline, we will measure age, race, gender,

level of education, income, employment, family size and household composition, height, weight, etiology of cirrhosis, liver disease severity (Child-Pugh score,⁶⁴ MELD score⁶⁵), Charlson comorbidity index,⁶⁶ medications, prior health care utilization, and reason for hospital admission.

3.4 Other Caregiver Measures: At baseline, we will measure age, race, gender, location (living with the patient or elsewhere), relationship to patient, and length of time caring for the patient.

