Prior to hospital discharge, the care coordinator will identify the primary care and/or hepatology provider of patients in the usual care group and will ensure follow up appointments at the time of hospital discharge. The coordinator will compose and send a letter to the primary care and/or hepatology provider summarizing the patient's diagnosis, hospital course, discharge medications, and the plan of follow-up care. If the patient does not already have a primary care or hepatology provider, the coordinator will work with the patient to identify a new provider. Subjects in this group will receive no further intervention.

Outcome Assessment (Both Arms)

Outcome measures will be obtained by blinded research staff from all enrolled subjects at baseline, 3 months, and 6 months. Baseline assessments will be completed in the hospital at the time of enrollment. Outcomes at 3 and 6 months will be completed in person. If participants are not able to attend in person, measures that can be performed remotely will be done via phone or videoconference.

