11.0 Statistical Considerations

This is a pilot trial for feasibility and effect size estimation. The plan is to enroll 40 total patients and randomize in 1:1 ratio to the Cirrhosis Medical Home and usual care. As a pilot trial, the study is not powered to test efficacy, but is designed to generate preliminary data to support a larger future trial. The sample size of 40, enrolled over 9 months (see study timeline in section 13), will allow for recruitment of approximately one patient/caregiver dyad per week. Data collected from this pilot will be used to provide an estimate of intervention effect, i.e. the difference in the primary outcome measure (SF-36) between intervention and control groups. The pilot data will also provide estimates on variability in the outcome measures in this patient population. The effect and variability estimates from the pilot data will be used to power a large trial. The sample size of 40 will provide 80% probability that the 95% confidence interval for the estimated treatment difference with half-width of 0.7SD will contain the true treatment effect. The pilot sample size of 40 has also been shown to minimize the overall sample size of the pilot and the main trial together with 80% power in the main trial to detect effect sizes in the range of 0.1~0.3SD.⁶⁷

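### Section 11 attaches its 80% to the wrong event: the figure matches the chance that the 95% CI half-width is at most 0.7SD with all 40 patients analysed, and nothing is allowed for missing 6-month SF-36

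*Combined protocol and SAP*

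**What the plan says.** Section 11.0 states: "The plan is to enroll 40 total patients and randomize in 1:1 ratio". It offers three reasons for that number: recruitment pace, a precision statement, and a published argument about minimising the combined size of pilot and main trial. The precision statement claims an "80% probability that the 95% confidence interval for the estimated treatment difference with half-width of 0.7SD will contain the true treatment effect". The same section disclaims power to test efficacy but adds: "The effect and variability estimates from the pilot data will be used to power a large trial". The effect in question is the between-arm difference in SF-36, and secondary objective 2.2.2 places it at six months after discharge.

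No expected rate of loss is given. Loss is nevertheless foreseen in several places:

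- Section 3.1.2 makes drop-out a primary feasibility measure: "The drop-out rate is the proportion of enrolled participants (patients and caregivers) who drop out of the study before completion".
- Section 3.1.3 provides for missing data: "For those with incomplete data, we will record reasons that data could not be collected".
- Section 3.2.6 tracks whether patients are "admitted with a COVID-19 diagnosis or die of COVID-19 while enrolled in the study", and section 3.2.8 records "completion of advanced directives, and place of death".
- Section 7.0 offers a fallback for missed visits: "If participants are not able to attend in person, measures that can be performed remotely will be done via phone or videoconference".

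**The concern.** The sentence mixes two properties of an interval. Coverage is fixed by the confidence level and does not depend on the sample size. Width depends on the sample size and, because the SD is estimated, is itself random. A sample-size argument based on precision has to be about width, yet the 80% is attached to coverage. A reader could conclude that the interval from this pilot is only 80% reliable, or could miss that 0.7SD is a bound on the width that will be met only with some probability.

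The statement is also made for the 40 enrolled, whereas the calculation behind it can only be for patients with a 6-month SF-36. It is the only one of the three reasons for 40 that says how precisely the pilot will estimate the effect meant to inform the main trial.

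**Working it through.** **Inputs.** 40 patients, 1:1, so 20 per arm; 95% interval; half-width 0.7SD; stated probability 80% (all section 11.0). Assumed here because the documents are silent: two-sided interval, unadjusted two-sample t comparison, common SD.

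**Half-width.** With n1 and n2 analysed, N = n1 + n2 and pooled sample SD s, half-width = t(0.975, N−2) × √(1/n1 + 1/n2) × s. At 20 per arm this is 2.024 × 0.3162 × s = 0.640s.

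**Reproducing the 80%.** The half-width is at most 0.7SD when s/SD ≤ 0.7/0.6402. Since 38s²/SD² follows a chi-square distribution on 38 df, P = P(χ²₃₈ ≤ 38 × (0.7/0.6402)²) = P(χ²₃₈ ≤ 45.4) = **81.0%**. With 39 analysed it is 77.1%, so 40 is the smallest total that reaches 80%.

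**Other readings of the sentence (20 per arm).**

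| Event | Probability |
|---|---|
| 95% CI contains the true effect | 95% by construction |
| Fixed ±0.7SD interval contains it: P(\|Z\| < 0.7/0.3162) | 97.3% |
| Half-width ≤ 0.7SD and CI contains it (integrating over s) | 76.4% |
| Half-width ≤ 0.7SD, given that the CI contains it: 0.764/0.95 | 80.4% |
| Half-width ≤ 0.7SD | 81.0% |

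Only the last two match 80%, and both are statements about width.

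**Effect of loss.** The half-width met with 80% probability is t(0.975, N−2) × √(1/n1 + 1/n2) × √(χ²₀.₈₀(N−2)/(N−2)), in SD units. At 20 per arm: 0.6402 × √(45.08/38) = 0.697. The loss rates below are assumptions, with loss equal in the two arms.

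| Analysed | Loss | P(half-width ≤ 0.7SD) | Half-width met with 80% probability |
|---|---|---|---|
| 40 | 0% | 81% | 0.70SD |
| 36 | 10% | 64% | 0.74SD |
| 32 | 20% | 44% | 0.79SD |
| 28 | 30% | 26% | 0.86SD |

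If 0.7 is read as rounded to one decimal, it survives down to 36 analysed (0.741) and first fails at 35 (0.75), a loss of 5/40 = 12.5%. Uneven loss is slightly worse: 20 against 12 analysed gives 0.82SD, compared with 0.79SD for 16 against 16.

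**Baseline adjustment.** Adjusting for baseline SF-36 with correlation ρ multiplies the SD by √(1−ρ²) and costs one degree of freedom. Restoring 0.70SD needs ρ = √(1 − (0.7/h)²), where h is the 80%-assured half-width on N−3 df: about 0.33 at 36 analysed, 0.48 at 32 and 0.58 at 28. The documents give neither an analysis model nor a correlation.

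**The case against.** The strongest reply is that little depends on this. The trial is a pilot with no efficacy test, its primary objective concerns screening and enrolment, and the main trial will be planned from the observed effect and SD, with the actual interval in hand. That is right, and it limits the consequence to the stated precision.

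A second reply is that the intended event is a reconstruction. That also stands. The sentence mentions both width and containing the true effect, so it may be a compressed form of the conditional statement (80.4%) rather than the unconditional one (81.0%). Either way the probability belongs to the width, and the sentence as printed does not say so.

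On loss, it is fair that a pilot which measures drop-out need not predict it, that 10% to 30% is an assumed range, and that moderate baseline correlation would recover the precision. The falling probabilities also look steeper than the widths because 0.7SD is treated as a hard threshold; 0.70 to 0.79SD at 20% loss is a modest change, and either is wide beside the 0.1 to 0.3SD effects that section 11.0 contemplates. None of this makes the figure apply to 40 enrolled. Remote assessment can recover patients who cannot attend, but not those who die or withdraw, and no adjusted analysis is specified.

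**Conclusion.** The concern holds. The sentence is wrong as written on every literal reading: 95%, 97.3% or 76.4%, not 80%. The sample size itself reproduces, since 20 analysed per arm is exactly what is needed for about 80% probability of a half-width no greater than 0.7SD. The error is therefore one of description, together with an unstated condition that all 40 patients are analysed without adjustment. There is no slack: one missing patient per arm lowers the probability from 81% to 73%, and an assumed 20% loss lowers it to 44%, with an 80%-assured half-width of 0.79SD. These loss figures assume equal SDs, an unadjusted comparison and equal loss in the arms. No participant, procedure or decision rule is affected.

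**What to change.** Replace the sentence in section 11.0 with wording such as:

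> *With 20 analysed patients per arm and an unadjusted comparison, there is about 80% probability that the half-width of the 95% CI for the treatment difference will not exceed 0.70SD; if 10%, 20% or 30% of patients lack a 6-month SF-36, the corresponding half-width is 0.74SD, 0.79SD or 0.86SD.*

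The essential part is the first clause: the correct event and the condition of 20 analysed per arm. The loss scenarios are assumptions and should be labelled as such; they let a reader see how firm the 0.70SD is. The cost is one sentence and a slightly less favourable stated precision. Enrolment stays at 40.

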12.0 Statistical Data Management

Primary data will be collected from conversations with the participants, both in person and via the telephone, as well as direct data capture from study instruments and the EMR and stored electronically in REDCap. The storage location will be backed up automatically, manually every day per REDCap standard procedures. Other data sources include outside medical record and lab data, data from INPC that will be stored in separate electronic files and merged with the primary data as needed. Quality assurance steps will include built in range checks and testing of database by study team prior to moving to production mode. The following quality control methods will be used:

single entry with random checks of accuracy and extraction and cleaning of data that will be used for analysis approximately every 6 months.

13.0 Privacy/Confidentiality Issues

All study visits will be conducted in a private room with the door closed. Nonetheless, there is a risk of loss of confidentiality. Risks will be mitigated by conducting study visits in a private location. All paper data will be stored in locked cabinets in a locked area. Electronic data are entered and stored into a password protected database. Only authorized personnel will have access to the study data, in both paper and electronic format.

14.0 Follow-up and Record Retention

Subject participation will last 6 months and the entire duration of the study should take about 2 years. Study records and study data will be retained and destroyed in accordance with federal, state, local, and university guidelines.

	Year 1				Year 2			
	1	2	3	4	1	2	3	4
Start-up								
Enrollment								
Intervention								
Outcome measures								
Data entry								
Data analysis								
R01 Preparation								

16.0 Appendices

16.1 Schedule of Events

16.2 Sample Care Plan

16.1 Schedule of Events

Assessment	Baseline	Initial Evaluation	First Visit	Second Visit	Week 4	CMH Interaction*					3 Month	CMH Interaction*					6 Month
Week [†]	0	0	72 hr	2		4	6	8	10	12		14	16	18	20	22	24
Demographics	X																
Height/weight	X																
Cirrhosis etiology	X																
MELD	X											X					X
Child-Pugh	X											X					X
CCI	X																
Medications	X		X	X		X	X	X	X	X		X	X	X	X	X	
Reason for admission	X																
SF-36	X				X							X					X
SPPB/LFI	X											X					X
C-SSRS				/		/	/	/	/	/		/	/	/	/	/	
PHQ-9	X											X					X
GAD-7	X											X					X
PHES	X											X					X
ZBI-12	X											X					X
Utilization	X																X
HABC-M Self		X ¹		X		X	X	X	X	X		X	X	X	X	X	
HABC-M Caregiver		X ¹		X		X	X	X	X	X		X	X	X	X	X	
MMSE		X ¹		/		/	/	/	/	/		/	/	/	/	/	/
TUG		X ¹		/		/	/	/	/	/		/	/	/	/	/	
HADS		X ¹		/		/	/	/	/	/		/	/	/	/	/	
PEG		X ¹		/		/	/	/	/	/		/	/	/	/	/	
3D CAM		X ¹		/		/	/	/	/	/		/	/	/	/	/	
Stroop		X ¹		/		/	/	/	/	/		/	/	/	/	/	
AUDIT-C		X ¹		/		/	/	/	/	/		/	/	/	/	/	
PACS		/ ¹		/		/	/	/	/	/		/	/	/	/	/	

*Interaction contacts may be in-person or via phone.

[†]Timing is approximate. The First Visit is within 72 hours of hospital discharge. The Second Visit is within 2 weeks of the First Visit. CMH Interactions occur a minimum of every 2 weeks.

X = required (HABC-M Caregiver only if caregiver enrolled)

/ = optional, depending on clinical circumstance

X¹ = can be performed at initial evaluation or first visit

 Performed by Blinded Research Staff for all enrolled subjects

 Performed by CMH Care Coordinator only for those randomized to the Cirrhosis Medical Home

 Patient assessments

 Caregiver assessments

Abbreviations: MELD, Model for End-Stage Liver Disease; CCI, Charlson Comorbidity Index; SF-36, Short Form Survey; SPPB, Short Physical Performance Battery; LFI, Liver Frailty Index; PHQ-9, Patient Health Questionnaire; GAD-7, Generalized Anxiety Disorder;; ZBI-12, Zarit Burden Interview; HABC-M, Healthy Aging Brain Care Monitor; MMSE, Mini-Mental Status Examination; TUG, Timed Up-and-Go; HADS, Hospital Anxiety and Depression Scale; PEG, Pain, Enjoyment, General Activity Scale; 3D CAM-, Confusion Assessment Method for the ICU

24. Reduce Anticholinergic Burden
25. Prescribe Anxiolytics
26. Prescribe Sleep Medication
27. Prescribe Other
